# 12.2 Institutional Review Board Monitoring

The Sponsor Investigator must obtain IRB approval for the investigation. Initial IRB approval, and all materials approved by the IRB for this study including the patient consent form and recruitment materials must be maintained by the Investigator and made available for inspection. Amendments will be submitted to the Nationwide Children's Hospital IRB for their review and approval prior to implementation. When an amendment to a protocol substantially alters the study design or increases potential risk to the study subject, the Informed Consent form will be revised and if applicable, subject's consent to continue participation will again be obtained.

## 13 STATISTICAL CONSIDERATIONS

For the secondary outcome measure of dystrophin expression, quantification of the number of fibers expressing dystrophin (determined by quantification of the number of fibers), measurement of the intensity of dystrophin staining at the sarcolemma (based on quantitative image analysis), and the degree of exon 2 skipping (as determined by RT-PCR) will be performed for each patient at each time point in a blinded fashion, and intra-patient comparisons of pre- and post-treatment values will be analyzed using repeated measures ANOVA with a Dunnett correction for multiple comparisons vs. baseline. For detecting change, we will have 80% power to detect a very large effect size (SMD=1.4-3.3, for sample sizes from 3-6).

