#### 4.2 Abstract

The proposed clinical trial is a systemic (intravenous) delivery of scAAV9.U7.ACCA for DMD patients with a duplication of exon 2 in the *DMD* gene. Preclinical data shows that the small nuclear RNA (snRNA) construct delivered by the scAAV9.U7.ACCA vector causes significant skipping of exon 2, resulting in exclusion of the exon from the mature messenger RNA (mRNA) with a high degree of efficiency, leading to mRNA containing only a single exon 2 (wild type [WT] mRNA) or no copies of exon 2 (Del2 mRNA). Translation of the wild-type mRNA results in entirely normal dystrophin protein, whereas translation of the Del2 mRNA via translational initiation of an internal ribosome entry sequence, or IRES) results in a highly functional isoform expressed in patients known to walk into their eighth decade.

The study is designed as an open-label trial to assess safety and obtain preliminary efficacy data. scAAV9.U7.ACCA will be delivered to the systemic circulation via peripheral limb vein. The subjects will receive a gene transfer dose of  $3 \times 10^{13}$  vector genomes per kilogram (vg/kg).

This is a phase I/IIa safety and tolerability study. Muscle biopsies will be performed by open biopsy at baseline and three months post-injection in the quadriceps muscles, and (using the needle biopsy approach outlined below) at 6 and 12 months post-injection in different quadriceps muscles (details of the muscle biopsy protocols, sites, and muscles chosen are found below in Section 10.1).

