## 5.2 Secondary Outcome

Secondary efficacy outcome measures: Muscle biopsy analysis for safety and dystrophin expression will be studied using multiple serial sections.

- a) Expression of dystrophin as demonstrated by immunofluorescent in staining with a dystrophin C-terminus antibody and the exon 1-encoded epitope antibody (Manex 1A) in muscle biopsy sections.
- b) Dystrophin protein expression quantified by western blot using a dystrophin C-terminus antibody and the exon 1-encoded epitope antibody (Manex 1A) and assessed by densitometry in muscle biopsy tissue.
- c) Percentage of exon 2 exclusion from the dystrophin mRNA transcript as measured by RT-PCR analysis.
- d) Transduction efficiency will be measured by qPCR of a U7-targeting sequence primer pair amplifying the DNA containing the U7snRNA, and expressed as vector genomes normalized to a single-copy genomic DNA control in each muscle sample.

For immunofluorescence, multiple serial sections will be studied. For each of these measures, statistical analysis based on differences between pre- and post-gene transfer muscle specimens will be analyzed using a paired t test (p < 0.05). Sections and western blots will be prepared by a single technician, who will blind the sample identifier; images will be obtained and expression assessed by another technician blinded to the sample time point. Quantification of immunofluorescent staining will be performed using a published protocol that has been used for comparisons between multiple labs with highly reproducible results, with the results

reported as membrane-localized dystrophin staining intensity relative to normal muscle sections. The muscle analysis of gene expression will occur without breaking the blind.

Splicing of exon 2 will be assessed by RT-PCR analysis, which will be performed under the same blinding regimen as used for protein expression studies. RT-PCR and data analysis will be performed under standardized protocols, resulting in quantification of unskipped (Dup2), wild-type (WT), and exon 2 deleted (Del2) transcripts. Notably, both WT and Del2 transcripts are therapeutic.

Transduction efficiency will be measured by qPCR of a U7-targeting sequence primer pair amplifying the DNA containing the U7snRNA, and expressed as vector genomes normalized to a single-copy genomic DNA control in each muscle sample.

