#### 6 STUDY DESIGN AND ENDPOINTS

## 6.1 Overall Study Design

The proposed phase I/IIa clinical trial is an open-label trial where subjects will take part in a single injection study of self-complementary AAV9 carrying the ACCA snRNA under the control of a U7 promoter (scAAV9.U7.ACCA) delivered one time through a peripheral vein of the DMD subjects.

The comparison of muscle tissue from baseline and 90 days post-gene transfer will be the basis of the secondary efficacy analysis. Upon completion of the 2-year study period, subjects will be monitored annually as per standard of care for up to 5 years.

There will be at least 6 weeks between dosing of the first and second subjects within the cohort. The allowance of 6 weeks between dosing of the first and second subjects in the cohort provides time for an DSMB review of the safety analysis from five time points (Days 1, 2, 7, 14 and 30) prior to dosing of the next subject.

Notably, we have not required a 30 day time point between subsequent subjects because we wish to accommodate the realistic possibility that siblings may both enroll in the study, and viral shedding might possibly expose the second of each sibling pair to the vector, generating antibodies that are exclusionary to the trial. We would consider the burden on families of living apart for six weeks to be excessive, and the prospect of making parents choose between one or another of their sons to enroll to be ethically untenable.

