## 6.3 Number of Subjects

Up to 3 DMD subjects matching the inclusion/exclusion criteria will be enrolled. Enrollment will be proceed as outlined in Section 6.4.

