## 10 PROCEDURE CRITERIA

# 10.1 Muscle biopsy

The baseline open muscle biopsy will be performed in one quadriceps muscle, or other appropriate muscle as determined by the SI. Another open muscle biopsy of the quadriceps, or other muscle as determined by the SI (biopsy will be in the contralateral leg to the pre-treatment biopsy, unless otherwise determined by the SI), will be performed 3 months post-infusion.

All open muscle biopsies will be performed under anesthesia, as per NCH standard clinical protocols.

Needle muscle biopsies of the quadriceps muscles (using the Vacora device; C.R. Bard, Inc.) will be performed at 6 and 12 months. In order to avoid resampling of the previous biopsy site, the open biopsies are anticipated to be performed in the vastus lateralis muscles, and the needle biopsies in the vastus medialis muscles. Every effort will be made to sample these same muscles in all subjects; however, in subjects (particularly older ambulant subjects) with limited quadriceps musculature, alternate muscle biopsy sites may be selected at the SI's discretion (including biceps, gastrocnemius, tibialis anterior or deltoid muscles).

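### Sections 5.2 and 13 name different tests for staining intensity and RT-PCR exon 2 skipping, and the power range extends to sample sizes that the trial cannot reach

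*Combined protocol and SAP*

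**What the plan says.** Section 5.2 lists four biopsy measures: immunofluorescence (reported as membrane staining intensity), western blot, RT-PCR exon 2 exclusion and qPCR. For each of them, it says, pre/post differences "will be analyzed using a paired t test (p < 0.05").

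Section 13, repeated in the synopsis, covers dystrophin-positive fibre number, staining intensity and RT-PCR skipping. It says that within-patient comparisons "will be analyzed using repeated measures ANOVA with a Dunnett correction for multiple comparisons vs. baseline". It then states that "we will have 80% power to detect a very large effect size (SMD=1.4-3.3, for sample sizes from 3-6").

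On sample size, Section 6.3 says "Up to 3 DMD subjects matching the inclusion/exclusion criteria will be enrolled", and the dosing table in Section 6.4 gives N as 1-3.

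On timing, Section 6.1 says "The comparison of muscle tissue from baseline and 90 days post-gene transfer will be the basis of the secondary efficacy analysis". Section 13 refers to every time point without listing them. Biopsies are open at baseline and 3 months, and by needle at 6 and 12 months (Sections 4.2 and 10.1).

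**The concern.** Two outcomes carry two tests. The direct conflict is limited to staining intensity and RT-PCR skipping. Western blot and qPCR have a test only in Section 5.2, and fibre number has one only in Section 13 and the synopsis.

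The two tests use different error terms and critical values, so with at most three subjects they can give different Day 90 answers from the same data. As written, the choice could be made after the data are seen.

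The power sentence stands next to the ANOVA but may not belong to it, and most of the sample sizes it covers are ruled out by the enrolment cap. At stake is how the efficacy result may be reported. Safety is the primary outcome.

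**Working it through.** **1. Reproducing the stated power.** Inputs from the plan: 80% power, p < 0.05, SMD 1.4-3.3, n = 3-6. Assumption: two-sided (not stated). For a paired t test, power = P(|T| > t(0.975, n-1)), where T is noncentral t with n-1 df and noncentrality SMD × √n. At n = 3 the critical value is 4.303 and the noncentrality at SMD 3.26 is 3.26 × 1.732 = 5.65, which gives 80%.

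| n | SMD for 80% power, paired t | power at SMD 3.3 | power at SMD 1.4 |
|---|---|---|---|
| 2 | 11.55 | 29% | 12% |
| 3 | 3.26 | 80.7% | 28.7% |
| 4 | 2.13 | 98.5% | 48% |
| 5 | 1.68 | >99% | 65% |
| 6 | 1.43 | >99% | 78.1% |

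The ends round to the stated 3.3 and 1.4. At n = 1 there are 0 df and neither test can be computed.

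**2. Other candidates for the same figure.** SMD for 80% power at n = 3 and n = 6:

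| method | n = 3 | n = 6 |
|---|---|---|
| one-sided paired t | 2.30 | 1.19 |
| normal approximation | 1.62 | 1.14 |
| paired t, Bonferroni for 3 | 5.67 | 1.88 |
| two-sample t | 3.07 | 1.80 |
| Dunnett, SD-of-change units | 2.36 | 1.43 |
| Dunnett, residual-SD units (× √2) | 3.34 | 2.02 |

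The Dunnett rows assume three post-baseline biopsies, sphericity and 3(n-1) error df (critical values 3.10 at 6 df and 2.61 at 15 df). Each Dunnett scale matches one end only. Of the methods tried, only the two-sided paired t matches both.

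**3. Does the choice of test change the Day 90 answer?** Simulation with n = 3, four biopsies, SD of the Day 90 change = 1, the same true effect at all three post-baseline biopsies, and 200,000 trials per setting (400,000 under the null). The documents give no covariance, so four structures were assumed. Entries are paired t power / Dunnett power / proportion of trials in which the tests disagree:

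| structure | 1.4 SD | 2.0 SD | 2.5 SD | 3.3 SD |
|---|---|---|---|---|
| compound symmetry | .287/.345/.249 | .471/.648/.313 | .622/.847/.293 | .806/.978/.183 |
| near-constant baseline (SD ratio 0.1:1) | .286/.224/.226 | .470/.476/.284 | .618/.692/.273 | .806/.911/.174 |
| needle SD 1.5× | .285/.190/.243 | .471/.430/.323 | .620/.651/.312 | .807/.895/.199 |
| needle SD 2× | .286/.101/.258 | .471/.261/.361 | .619/.444/.381 | .806/.732/.280 |

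Disagreement in this range is 17-38%. At larger effects it falls to 9-15% at 4 SD, about 2-4% at 5 SD and under 1% at 6 SD. Under the null, at least one test is significant at Day 90 in 5.2-6.0% of trials, against 5.0% for the paired t test alone.

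**The case against.** The strongest reply is that the two passages divide the work: the paired t test for Day 90, and the ANOVA for the whole series. That would be coherent. Section 6.1 makes Day 90 the efficacy basis, repeated measures ANOVA on two time points is the paired t test, and Dunnett has a role only with several comparisons. But no passage states this split. Section 5.2 does not restrict its test to Day 90, and Section 13 does not exclude Day 90. The reply shows that the gap may be unstated scope rather than rival analyses; it does not close the gap.

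Several stronger readings are tempting and are not supported:

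- A reader might infer that the power sentence was certainly computed for a paired t test. The plan names no test, sidedness or SMD scale, and at n = 6 the paired t and Dunnett (compound symmetry) powers at SMD 1.4 are almost equal (.781 and .784). The attribution rests on matching both ends.
- A reader might infer that the plan claims an SMD of 1.4 is detectable with three subjects. The sentence is more naturally read as pairing the larger SMD with the smaller n, and its n = 3 end is right for a paired t test. The fault is the part for n = 4-6.
- A reader might infer that the tests will usually conflict. That depends on the true effect, and the documents give no expected effect in SD units.
- A reader might infer that the paired t test is the more powerful whenever needle samples are noisier. At 1.5× Dunnett still leads at 2.5 SD (.651 vs .620) and at 3.3 SD (.895 vs .807).

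**Conclusion.** The inconsistency stands and should be fixed. The textual conflict, and the mismatch between n = 3-6 and a cap of 3, follow directly from the documents. That the power figure comes from a two-sided paired t test is a well-supported inference.

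The size is moderate and rests on assumptions. The disagreement rates depend on invented covariances, complete data from three subjects and an equal effect at every post-baseline biopsy. Picking whichever test is significant adds at most about one percentage point to the Day 90 false-positive rate. The cost is therefore an ambiguous result rather than serious error inflation. No p-value from these outcomes drives dosing, enrolment or stopping.

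**What to change.** Reconcile Section 5.2, Section 13 and the synopsis to one prespecified test for Day 90 versus baseline. The paired t test is the simplest choice, because Section 5.2 already names it and it reproduces the stated power. The documents do not compel it. State power for n = 3 only (80% at an SMD of about 3.3, two-sided) and delete the n = 4-6 range. Say that results are descriptive if too few subjects are treated to compute the test.

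Report Months 6 and 12 as supportive. Those needle samples are taken "at 6 and 12 months post-injection in different quadriceps muscles", and Section 10.1 says "the open biopsies are anticipated to be performed in the vastus lateralis muscles, and the needle biopsies in the vastus medialis muscles", so a change from baseline there also reflects technique and muscle. The documents give no size for that shift.

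Cost: wording only, with no new samples or visits. There would be no formal p-value at Months 6 and 12. Day 90 power would be lower than with ANOVA-Dunnett under several plausible covariances: 47% versus 65% at 2 SD under compound symmetry, and at 3.3 SD Dunnett leads in three of the four structures tried.

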#### 5 OBJECTIVES AND PURPOSE

## **5.1 Primary Outcome**

Safety is the primary outcome for this clinical gene transfer trial. Stopping criteria are based on development of unacceptable toxicity defined as the occurrence of two or more unexpected Grade III or higher treatment-related toxicities.

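### The only power statement covers 3 to 6 subjects, but the trial can enrol only 1 to 3: the SMD of 1.4 is out of reach, N = 2 has no figure, and at N = 1 neither named test can be run

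*Combined protocol and SAP*

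**What the plan says.** Section 13 gives the plan's only power statement, and the Statistical Analysis row of the synopsis (Section 1) repeats it: "we will have 80% power to detect a very large effect size (SMD=1.4-3.3, for sample sizes from 3-6"). SMD is not defined, and sidedness is not given.

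Section 6.3 sets the cap: "Up to 3 DMD subjects matching the inclusion/exclusion criteria will be enrolled". The Sample Size row of the synopsis, directly above the power sentence, gives N = 1-3, as do Sections 6.4, 8.1 and 9.1.2.2.

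Two analyses are named for the same secondary measures. Section 5.2 says that pre/post differences "will be analyzed using a paired t test (p < 0.05"). Section 13 names repeated measures ANOVA with Dunnett's correction against baseline. Biopsies are taken at baseline and at 3, 6 and 12 months (Sections 4.2 and 10.1). Section 6.1 singles out one contrast: "The comparison of muscle tissue from baseline and 90 days post-gene transfer will be the basis of the secondary efficacy analysis".

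The primary outcome lies elsewhere: "Safety is the primary outcome for this clinical gene transfer trial" (Section 5.1).

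**The concern.** The power statement and the enrolment limits describe different trials. Sample sizes of 4, 5 and 6 cannot occur. Sizes of 1 and 2 can occur and have no figure. A reader of Section 13 may take an SMD of 1.4 as within the trial's reach, when the plan pairs it with a sample size that it does not allow.

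The statement also cannot be tied to an analysis. SMD may mean mean change over the SD of change, or over the within-subject SD, and two tests are named. A reader cannot tell which analysis the 80% supports.

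At stake is how the dystrophin and exon-skipping results are read. If a non-significant result from 2 or 3 boys is set beside a claim of 80% power down to 1.4, it may be taken as evidence of little effect. If one boy is treated, the named analyses yield nothing, and what is reported would have to be decided after the data are seen.

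**Working it through.** **Inputs.** Power 80% and SMD 1.4-3.3 for n = 3-6 (Sections 1 and 13); alpha 0.05 (Section 5.2); enrolment 1-3 (Sections 1, 6.3 and 6.4); patient as the unit, one value per time point (Section 13); three post-baseline biopsies (Section 10.1). *Assumed:* two-sided testing; SMD d = mean change / SD of change; sphericity for the ANOVA.

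**1. Reproduce the stated range.** For a paired t test, df = n − 1 and the noncentrality is d√n. Power is the probability that a noncentral t exceeds the two-sided 5% critical value in absolute size. Solving for 80%:

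| n | Permitted? | SMD for 80% power | Power at SMD 1.4 |
|---|---|---|---|
| 1 | yes | none (df = 0) | none |
| 2 | yes | 11.55 | 12.5% |
| 3 | yes | 3.26 | 28.7% |
| 4 | no | 2.13 | 48.3% |
| 5 | no | 1.68 | 65.4% |
| 6 | no | 1.43 | 78.1% |

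The ends, 3.26 and 1.43, match the stated 3.3 and 1.4. Conversely, SMD 3.3 has 80.7% power at n = 3, and SMD 1.4 has 78.1% at n = 6. Simulation at the solved SMDs for n = 2, 3 and 6 gave 80.0-80.1% power. Other readings do not fit both ends (n = 3 / n = 6): one-sided paired t 2.30 / 1.19; normal approximation 1.62 / 1.14; independent two-sample t 3.07 / 1.80. So the stated figures are sound arithmetic for a two-sided paired t test, but only n = 3 lies within the permitted enrolment.

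**2. Same check under the Section 13 analysis.** Error df = 3(n − 1), with simulated Dunnett critical values of 4.27, 3.10 and 2.61 for n = 2, 3 and 6. Power is per comparison.

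| n | SMD for 80%, SD-of-change units | Within-subject-SD units (× √2) |
|---|---|---|
| 2 | 3.92 | 5.54 |
| 3 | 2.36 | 3.34 |
| 6 | 1.43 | 2.02 |

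The first convention matches the stated end at n = 6 and the second matches the end at n = 3. Neither matches both.

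**3. Power within permitted enrolment (SD-of-change units).**

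- N = 3, SMD 1.4: 28.7% (paired t) or 34% (Dunnett, one comparison). If the same shift of 1.4 held at all three biopsies, the chance that at least one Dunnett comparison is significant would be 52%. That does not apply to the single baseline versus Day 90 contrast.
- N = 2, SMD 3.3: 28.6% (paired t) or 66% (Dunnett).
- N = 1: error df = 1 − 1 = 0 for the paired t, and 3 × (1 − 1) = 0 for the ANOVA. Neither test can be computed.

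Withdrawal after gene transfer ends required biopsies (Section 7.2), so the number of evaluable pairs can fall below the number enrolled.

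**The case against.** The plan does not claim 80% power for SMD 1.4 with 3 subjects. Its range pairs 3.3 with n = 3 and 1.4 with n = 6, and the n = 3 figure is correct under the paired t test. That stands: this is not an arithmetic error. The fault is that 1.4 is offered for a size the trial cannot have, while sizes it can have are left blank.

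The consequence is also limited. The outcome is secondary in an open-label safety trial, the plan itself calls the detectable effect very large, and no enrolment or stopping decision is derived from the sentence. This stands too, and it limits the severity.

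At N = 1 a test could be computed by treating the serial sections of Section 5.2 as replicates. That would compare sections within one boy and support no inference beyond him. Section 13 describes measurement per patient and time point, so the claim holds with the patient as the unit of analysis.

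The Dunnett figures depend on sphericity, which 2 or 3 subjects cannot check. Section 10.1 expects an open biopsy of one quadriceps muscle at 3 months and needle biopsies of another at 6 and 12 months, so equal variances are not assured. Those figures are indicative. The contradiction between 3-6 and 1-3 does not depend on them.

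Finally, a detectable SMD of 11.5 at N = 2 may look like false precision. Reporting N = 2 descriptively would be a reasonable alternative. Leaving it unaddressed is not.

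**Conclusion.** The concern holds. The power statement is inconsistent with the design: 3 is the only sample size common to the stated range and permitted enrolment, and the SMD of 1.4 requires 6 subjects, twice the maximum. At N = 3 the detectable SMD at 80% power is 3.26 (paired t) or 2.36 (Dunnett), and power for 1.4 is about 29% or 34% per comparison. At N = 2 the detectable SMD is about 11.5 or 3.9. At N = 1 no named test exists and no alternative is given.

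These sizes assume two-sided 5% testing, SMD in SD-of-change units and, for Dunnett, sphericity. The mismatch between the two ranges needs none of these assumptions. It should be fixed; because the outcome is secondary, it does not put the trial's primary aim at risk.

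**What to change.** In Sections 1 and 13, remove the SMD of 1.4 and the sample sizes 3-6. Then:

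- Name one test for these measures, reconciling Section 5.2 with Section 13, and state alpha and sidedness.
- Define SMD and say that power is per comparison.
- Give detectable effects for permitted N only. If the paired t test is kept: N = 3, 80% power for SMD 3.3; N = 2, about 11.5; N = 1, no test. If Dunnett is kept (SD-of-change units, sphericity assumed): N = 3, 2.4; N = 2, 3.9; N = 1, no test.
- State that at N = 1 individual pre- and post-treatment values are reported without a p-value, and that a non-significant result at N = 2 or 3 is not evidence of no effect.

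The cost is wording in Sections 1, 5.2 and 13. Under the paired t test the stated sensitivity becomes less favourable. No extra patients or biopsies are needed.
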